 - a. Overall number of parathyroid glands identified (Experimental Group: Glands identified with naked eye + NIRAF; Control Group: Glands identified with naked eye) [Time Frame: Immediate. During PTx procedure.]
- 5. Number of parathyroid glands identified with NIRAF
 - a. Number of parathyroid glands identified with NIRAF, which was not seen with surgeon's naked eye [Time Frame: Immediate. During PTx procedure.]
- 6. Number of diseased parathyroid glands identified versus preoperatively localized glands
 - a. Number of diseased parathyroid glands identified intra-operatively versus glands localized preoperatively using sestamibi, CT or ultrasound [Time Frame: Preoperative to immediate during PTx procedure.]
- 7. Number of intra-operative parathyroid hormone (PTH) assays sent
 - a. Number of intra-operative parathyroid hormone assays sent during the procedure [Time Frame: Immediate. During PTx procedure.]
- 8. Duration taken to identify first parathyroid gland
 - a. Duration taken to identify 1st parathyroid gland in PTx procedure – timed from skin incision to finding PG. [Time Frame: Immediate. During PTx procedure.]
- 9. Duration taken to identify last parathyroid gland
 - a. Duration taken to identify last parathyroid gland in PTx procedure – timed from skin incision to finding the last PG. [Time Frame: Immediate. During PTx procedure.]
- 10. Duration of parathyroidectomy (PTx) procedure
 - a. Duration of PTx procedure – timed from skin incision until the surgeon notifies the anesthesia team to awaken the patient [Time Frame: Immediate. During PTx procedure.]
- 11. Duration taken for intraoperative parathyroid hormone (PTH) to normalize
 - a. Time taken for PTH to attain cure criteria or normalize - timed from skin incision until the PTH levels drops > 50% of its baseline value and/or PTH drops < 65 pg/ml or 6.9 pmol/L. [Time Frame: Immediate. During PTx procedure.]
- 12. Number of nights spent in the hospital after parathyroidectomy
 - a. Number of nights spent for postoperative recovery in the hospital after the surgical procedure. [Time Frame: 0-72 hours after PTx procedure.]
- 13. Number of 'false positive' tissues excised by surgeon
 - a. Number of tissues that were excised by surgeon assumed to be parathyroid tissue, but is later validated as nonparathyroid tissue (false positive) by histology [Time Frame: Immediate to 10 days after PTx procedure.]
- 14. Number of doctor visits/emergency department visits or hospital admissions

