3.0 Animal Studies and Previous Human Studies

Modalities that rely on NIRAF detection for label-free parathyroid identification have been successfully validated in several studies (15-18). FDA approval for this application was recently granted to Fluobeam (a commercially available imaging system) and PTeye (a commercial fiber probe-based system) in 2018 (14). Certain outcome studies have reported that imaging-based systems for NIRAF detection such as the PDE Neo II system was able to reduce the number of frozen sections (or PTH aspirate) required during parathyroid procedures (17). However, other studies have reported that they observed no benefit from imaging-based systems in parathyroid localization (19). In a recent study, Thomas *et al.* demonstrated that a fiber probe-based system – the PTeye – was more sensitive in parathyroid identification compared to the imaging-based system by PDE Neo II (20). To date, there has been no studies that determine the impact of a fiber probe-based system (i.e. PTeye) during parathyroid surgeries in minimizing a number of frozen sections (or PTH aspirate) obtained intraoperatively or postsurgical complications.

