6.0 Study Procedures

For patients assigned to the study arm, the surgeon will use the PTeye as an intraoperative tool to identify if a suspect tissue is a parathyroid or not, during the parathyroid surgery. The surgeon will first take 5 baseline NIRAF measurements on the thyroid gland (or neck muscle, if thyroid is absent) using the disposable sterile fiber probe that is connected to the PTeye console (see Figure 1), as per device functionality requirements. The subsequent step would involve touching the target tissue in the neck with the fiber optic probe, following which the PTeye will indicate to the surgeon if the tissue is parathyroid or not. Parameters which are displayed on the PTeye console – Baseline values, Detection Intensity, Parathyroid Detection Ratio – will be recorded for each patient enrolled in the study arm. PTeye indicates that a tissue is parathyroid if it displays the 'Parathyroid Detection Ratio' is greater than 1.2. The rest of the surgical procedure will follow according to standard protocol.

For patients assigned to the control arm, the surgeon will not use the PTeye and will proceed with the parathyroid surgery as usual, while relying solely on her/his surgical experience in identifying the parathyroid glands during the operations.

Figure 1. A commercial fiber probe-based system (PTeye, [REDACTED]) for detecting near infrared autofluorescence (NIRAF) utilized for intraoperative parathyroid gland identification. PTeye consists of 1) the console that has a display and indicates to the surgeon if a tissue is parathyroid or not, 2) a detachable fiber optic probe, and 3) a foot-pedal which is activated by the surgeon for tissue NIRAF measurements.

De-identified information regarding (i) patient demographics, (ii) duration of surgery, (iii) number of frozen section (or PTH aspirate) analysis performed, (iv) frozen section (or PTH aspirate) and permanent histology reports of all excised tissues, (v) blood calcium levels (before surgery, 5-14 days after surgery and 6 months after surgery), (vi) parathyroid hormone (PTH) levels (5-14 days after surgery and 6 months after surgery) and (vii) postsurgical complications, if any and history of ER visits or hospitalization or repeat surgeries due to high or altered calcium levels, will be compiled for all enrolled patients. These parameters would then be compared between the study arm and the control arm to truly gauge the impact or value of a device like PTeye for parathyroid surgeries.

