10.0 Statistical Considerations

Currently there are no comparable published randomized trials that have evaluated the effect of NIRAF detection for reducing intraoperative frozen section analysis (or PTH aspirate) during parathyroidectomies. Based on preliminary data obtained from a similar ongoing study at Vanderbilt University Medical Center over 123 patients, an 83% reduction in frozen section analysis was observed in the interventional group of 63 patients where NIRAF was used, compared to the control group of 60 patients where NIRAF was not used (unpublished). The mean frozen section analysis (FSA) obtained for the NIRAF group is 0.1 FSA/patient versus 0.6 FSA/patient obtained in the control group. Assuming, that an expected mean difference of 0.6 FSA/patient needs to be observed between the NIRAF and the control group, where the standard deviation of the enrolled study population is 0.8 (Standard Deviation obtained in VUMC study population is 0.78 FSA/patient), 47 patients would be required per group (for a 95% powered study). Since this study may involve patient follow-up for data up to 6 months after surgery, we will thus assume an approximate data attrition rate of 15%, thus requiring a recruitment of 55 patients per group. Therefore, a total of 110 patients (study and control arm) should be recruited per surgeon for this study at this study site. Overall, 110

patients need to be enrolled at this study site under a single surgeon to assess the impact of this technology.

Sample size	
2-side significance level	0.05
Power (1-beta)	0.95
Ratio of sample size, Control/NIRAF group	1
Expected mean in NIRAF group	0.7
Expected mean in Control group	0.1
Study population standard deviation	0.8
Result	
Sample Size - Control group	47
Sample Size - NIRAF group	47
Sample Size – Control group compensated for 15% attrition	55
Sample Size – NIRAF group compensated for 15% attrition	55
Total sample size	110

Analysis Plan:

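### Secondary outcome 5 credits NIRAF with glands not seen by eye, but PTeye is a contact probe used on tissue already in view, and no by-eye call before probing or confirmation standard is specified

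*Combined protocol and SAP*

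**What the plan says.** Section 2.0 defines secondary outcome 5 as "Number of parathyroid glands identified with NIRAF, which was not seen with" the surgeon's unaided eye. It does not say what counts as seen. Outcome 4, just above it, is the total number of glands identified in each arm: "Experimental Group: Glands identified with naked eye + NIRAF; Control Group: Glands identified with naked eye".

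Section 3.0 sets "PTeye (a commercial fiber probe-based system") apart from imaging systems. In Section 6.0, "the surgeon will use the PTeye as an intraoperative tool to identify if a suspect tissue is a parathyroid or not", and the step itself is "touching the target tissue in the neck with the fiber optic probe". The console then tells the surgeon whether the tissue is parathyroid (detection ratio above 1.2). The device data to be kept are listed: "Baseline values, Detection Intensity, Parathyroid Detection Ratio – will be recorded for each patient enrolled in the study arm". The surgeon's own impression before probing is not on that list. Pathology reports are compiled for excised tissue.

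Section 10.0 places the study under one surgeon, and its analysis plan compares the NIRAF and control groups on primary and secondary outcomes, with no exception for outcome 5.

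**The concern.** The definition fits an imaging device that reveals glands the eye has missed. A contact probe works the other way round: the surgeon sees a piece of tissue, wonders what it is, and touches it. What such a device can add is mainly recognition, not visibility.

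Aim (i) in Section 2.0 asks whether PTeye helps to identify parathyroid tissue during surgery. Outcome 5 is the only listed outcome that attributes individual glands to the device within a patient. If its rule is unclear, a low count could be reported as no added value when it only reflects a strict reading, and a high count could reflect generous attribution after the console has answered. The surgeon's prior impression cannot be reliably rebuilt afterwards, so the gap has to be closed before patients are operated on.

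**Working it through.** **Plan figure.** The documents give no expected value for outcome 5. The only figure used here is the arm size. For the primary outcome, n = 2(1.960 + 1.645)² × 0.8² / 0.6² = 46.2, so 47 per group, as stated. The planned 55 matches 47 × 1.15 = 54.05, rounded up. Dividing instead, 47 / 0.85 = 55.3, gives 56; the difference is immaterial here.

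**Scoring sample records.** Four hypothetical probed tissues, all with a ratio above 1.2:

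| By-eye view before probing | Pathology | Seen = visible | Seen = recognised |
|---|---|---|---|
| Taken for a lymph node | Parathyroid | 0 | 1 |
| Uncertain | Parathyroid | 0 | 1 or 0; no rule for uncertain |
| Sure it is parathyroid | Parathyroid | 0 | 0 |
| Taken for other tissue | None obtained | 0 | Unsettled; no confirmation standard |

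Under the first reading every tissue that is targeted and touched has ordinarily been seen, so every record scores 0. A gland hidden beneath other tissue might occasionally count, hence near zero rather than exactly zero. Under the second reading the score depends on the first column, which is not among the device data Section 6.0 lists, and in the last row on a confirmation rule that is not stated.

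**Spread between readings (illustrative; g and q are assumptions, not document figures).** Expected total = N × g × q, with N = 55 NIRAF patients, g glands probed per patient and q the share credited as not seen. With g = 2:

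- q = 0: 55 × 2 × 0 = 0
- q = 1%: 55 × 2 × 0.01 = 1.1; chance of a total of zero, treating glands as independent, 0.99¹¹⁰ = 33%
- q = 5%: 5.5
- q = 10%: 11
- q = 20%: 22

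At q = 5%, moving g from 1 to 4 moves the total from 2.8 to 11. So the same operations could give none or about twenty, depending on how one word is applied.

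**Comparison by arm.** Controls have no NIRAF reading, so outcome 5 is zero there by construction. A between-group test of it, as the analysis plan implies, would carry no information.

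**The case against.** The strongest reply is that the outcome counts glands, not tissue. A surgeon who takes a nodule for a lymph node has seen tissue but has not seen a parathyroid gland, so a positive reading would score 1. The documents lend this support: outcome 4 speaks of glands identified by eye, and Section 1.0 treats the surgeon's visual task as identification. This stands, and a reader should not infer that outcome 5 must come out at zero. That result belongs to the literal reading only.

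A reader might also infer that the trial cannot show added yield. It can: outcome 4 compares total glands between randomised arms, and the total does not depend on which glands are credited to the eye and which to the probe. For the same reason outcome 4 does not share this defect. Outcomes 8, 9 and 13 (times to first and last gland, false-positive excisions) also bear on identification.

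It is also fair to say that this is one of 15 secondary outcomes and carries no power claim.

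What the reply does not cure is scoring. Reading seen as recognised makes the outcome sensible, but then it needs a by-eye call fixed before the probe is applied and a standard for what counts as parathyroid. The documents supply neither.

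**Conclusion.** The point holds for outcome 5 alone. On the literal reading it would be near zero; on the more natural reading it rests on one unblinded surgeon's attribution, potentially made after the console result, and a device-positive reading could count as a gland with nothing to confirm it. Either way the number has no fixed meaning.

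Its size cannot be taken from the documents. The 0 to 22 range rests on assumed values for glands probed and share credited, and shows how far the readings can diverge. A reader might infer that some definite number of glands would be lost; the documents do not support that, because they give no rate and do not settle the reading.

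The primary outcome, its analysis and the sample size are unaffected. The change is still worth making before enrolment, because the missing call cannot be reliably recovered after surgery.

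**What to change.** - Add one field per probed tissue, completed before the probe is applied: the surgeon's by-eye class (parathyroid, not parathyroid, uncertain).
- Redefine outcome 5 as the number of tissues classed by eye as not parathyroid or uncertain that PTeye read as parathyroid (ratio above 1.2, the threshold in Section 6.0) and that pathology already obtained (histology, frozen section or aspirate) confirmed as parathyroid.
- Report device-positive tissue without pathology separately as unconfirmed. Send no extra samples for this purpose: frozen sections and aspirates are the primary outcome, so added sampling would distort it.
- Report outcome 5 descriptively within the NIRAF arm, per patient and per tissue probed, and exempt it from the between-group tests in Section 10.0.
- Leave outcome 4 as it is.

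The cost is a wording change and one entry per probed tissue beside the PTeye readings already recorded. The drawback is that glands left in place without pathology drop out of the confirmed count, so it may understate yield; the separate unconfirmed count keeps them visible.

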2.0 Rationale and Specific Aims

The goal of this study is to assess whether using PTeye – a NIRAF detection modality – can reduce healthcare associated costs after parathyroid surgeries and improve patient outcomes. The specific aims of this study is to determine if PTeye is beneficial or not for (i) intraoperative identification of parathyroid tissues, (ii) improving efficiency of parathyroid surgeries, and (iii) minimizing risk of postsurgical complications.

By being able to quickly and definitively locate parathyroid glands while in the operating room, the duration of surgical procedure could be further reduced. In addition, the number of frozen section biopsy (or PTH aspirate) and associated costs can be minimized. Furthermore, repeat surgeries as a result of missing a diseased parathyroid gland at the time of the initial parathyroidectomy for hyperparathyroidism could potentially be avoided.

Primary Outcome Measure:

1. Number of frozen sections (or PTH aspirate) sent for analysis
 - a. Number of frozen sections (or PTH aspirate) sent for analysis during the procedure to confirm potential parathyroid tissue [Time Frame: Immediate. During PTx procedure.]

Secondary Outcome Measure:

1. Persistent hyperparathyroidism (Immediate)

- a. Failure of intra-operative parathyroid hormone (PTH) to normalize (defined as failure of PTH to drop > 50% of its baseline value at final intra-operative PTH assay and/or failure of PTH to drop < 65 pg/ml or 6.9 pmol/L). [Time Frame: During parathyroidectomy (PTx) procedure]
- 2. Persistent hyperparathyroidism or hypercalcemia (transient)
 - a. Elevated blood calcium levels (total blood calcium level > 10.5 mg/dL or 2.6 mmol/L) with/without elevated parathyroid hormone (PTH) (serum intact PTH > 65 pg/ml or 6.9 pmol/L) at first postoperative visit. [Time Frame: 5-14 days after PTx procedure]
- 3. Persistent hyperparathyroidism or hypercalcemia (failed parathyroidectomy)
 - a. If blood calcium with/without parathyroid hormone (PTH) has not normalized at 1st post-operative visit, calcium and/or PTH is subsequently measured as necessary. Patient is defined to have a failed parathyroidectomy if hypercalcemia/hyperparathyroidism (defined as total blood calcium level > 10.5 mg/dL or 2.6 mmol/L, with/without elevated serum intact PTH > 65 pg/ml or 6.9 pmol/L) persists at or after the 6th postoperative month. [Time Frame: 6 months after PTx procedure]
- 4. Overall number of parathyroid glands identified

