- a. Number of doctor visits/emergency department visits or hospital admissions due to persistent hypercalcemia and/or associated symptoms after parathyroidectomy procedure [Time Frame: Up to 6 months after PTx procedure.]
15. Number of patients who have had repeat parathyroidectomy (PTx) procedure
 - a. Number of patients with repeat PTx procedure performed after the current procedure [Time Frame: 6 - 12 months after PTx procedure.]

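### Repeat parathyroidectomy is framed at 6–12 months and failure is judged only from month 6, so an early, successful reoperation may count in neither outcome

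*Combined protocol and SAP*

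**What the plan says.** Section 2.0 lists two secondary outcomes that bear on a failed operation and its consequence.

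- Outcome 3 (failed parathyroidectomy) requires raised calcium, with or without raised PTH, that "persists at or after the 6th postoperative month". Its time frame is 6 months.
- Outcome 15 (repeat surgery) is worded as "Number of patients with repeat PTx procedure performed after the current procedure". The wording has no lower time limit, but the frame attached to it is "Time Frame: 6 - 12 months after PTx procedure".

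The data schedule is described in two other places. Section 10.0 justifies the attrition allowance with "Since this study may involve patient follow-up for data up to 6 months after surgery". Section 6.0 places the last scheduled calcium and PTH values at 6 months. It also says that "history of ER visits or hospitalization or repeat surgeries due to high or altered calcium levels, will be compiled for all enrolled patients", with no time window. Outcome 14 (visits and admissions) stops at 6 months. Section 12.0 gives a study duration of about two years but describes no contact with individual patients at month 12.

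No section says how a patient reoperated before month 6 is classified for outcome 3 or outcome 15.

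**The concern.** Reoperation for persistent disease within the first six months is direct evidence that the index operation failed. Outcome 3 looks at the patient's state at or after month 6, by which time a successful second operation has removed the evidence. Outcome 15 should catch the event, but its stated frame opens only at month 6. Read literally, a failed index operation that was corrected early appears as a success on both outcomes.

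Avoiding repeat surgery after a missed diseased gland is part of the rationale in section 2.0, and these two outcomes measure it most directly. Events will be few, so the classification of one or two patients matters to the reported rates. The surgeon necessarily knows the arm, since the device is used in one arm and not in the other. A count that depends on when a reoperation takes place should therefore be settled by a rule fixed in advance.

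**Working it through.** **The plan's own figure.** The only sample-size calculation is for the primary outcome (section 10.0: difference 0.6, SD 0.8, two-sided 0.05, power 0.95). Per group, n = 2(1.960 + 1.645)² × 0.8² / 0.6² = 2 × 13.0 × 0.64 / 0.36 ≈ 46.2, rounded up to 47, which matches. The plan then recruits 55 per group, 110 in total. That outcome is measured during surgery, so nothing below affects it. No event count or power is stated for outcomes 3 or 15.

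**The windows side by side.** Described follow-up covers months 0–6. The frame of outcome 15 covers months 6–12. They meet only at month 6.

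**How each course is classified.** The frame of outcome 15 can be read in two ways: as the interval in which the reoperation must occur, or as the time at which repeat-surgery status is assessed.

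| Course after the index operation | Outcome 3 | Outcome 15, frame as event window | Outcome 15, frame as time of assessment |
|---|---|---|---|
| Reoperated before month 6, normal from month 6 | Not failed | Not counted | Counted |
| Reoperated before month 6, still abnormal at month 6 | Failed | Not counted | Counted |
| Abnormal at month 6, first reoperated in months 6–12 | Failed | Counted, if ascertained | Counted, if assessed after the reoperation |
| Abnormal at month 6, never reoperated | Failed | Not counted | Not counted |

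Only the first row can be missed by both outcomes, and only under the event-window reading. Outcome 3 misses that row under either reading.

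**Scale.** Inputs: failure in 5–10% of cases (section 1.0, a background figure, applied here to this trial as an assumption) and 110 patients (section 10.0). The share of failures reoperated successfully before month 6 is not in the documents; 10–50% is assumed as a range.

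- Expected failures: 110 × 0.05 = 5.5 to 110 × 0.10 = 11, or 2.75 to 5.5 per arm of 55.
- Missed, at a 10% share: 5.5 × 0.10 = 0.55 to 11 × 0.10 = 1.1.
- Missed, at a 50% share: 5.5 × 0.50 = 2.75 to 11 × 0.50 = 5.5.
- Overall range: about 0.6 to 5.5 patients across both arms.
- Each patient reclassified moves an arm's rate by 1/55 = 1.8 percentage points, or 1/47 = 2.1 points if 47 per arm have data.

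**The case against.** The strongest reply is that the 6–12 month frame states when status is ascertained. The definition has no lower limit, and the protocol uses time frames in that sense elsewhere: outcome 13 concerns tissue removed during surgery, but its frame runs to 10 days so that histology can report. On that reading an early reoperation is counted under outcome 15. This is a fair reading and the text does not exclude it. The text does not establish it either, because the neighbouring outcome 14 uses a cumulative frame (up to 6 months), which makes a lower bound of 6 look deliberate. It also leaves outcome 3 as it stands, and it leaves an assessment time anywhere between months 6 and 12 with no contact described after month 6.

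It can also be said that a frame starting at month 6 follows from the protocol's decision not to define failure before then. That explains the wording, but it does not say where an earlier reoperation belongs.

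Three stronger inferences are tempting, and the documents do not support them.

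- A reader might infer that every reoperation before month 6 escapes both outcomes. It does not: a patient still abnormal at month 6 meets outcome 3.
- A reader might infer that these events go unrecorded, or that nothing is collected in months 6–12. Section 6.0 compiles repeat surgeries with no time limit, and the month-6 phrase in section 10.0 explains an attrition allowance; it does not set an end of follow-up. What can be said is that no contact after month 6 is described.
- A reader might infer that early failures appear nowhere as failures. Outcome 1 (intraoperative PTH) and outcome 2 (calcium at 5–14 days) may flag them, and a related admission may fall under outcome 14. Outcome 2 is labelled transient, however, so it would not present the patient as a failed operation.

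**Conclusion.** The point holds in a limited form. The frame of outcome 15 does not match the described follow-up schedule, and no rule covers reoperation before month 6. Outcome 3 as written scores an early, successfully corrected failure as a success, however outcome 15 is read. Outcome 15 omits the same patient only if its frame is the event window, which the text leaves open.

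The size is uncertain: about 0.6–5.5 of 110 patients, resting on the background 5–10% failure rate and an assumed 10–50% early, successful reoperation. The documents give no split by arm, so the direction of any effect on the comparison is unknown. A specific claim, such as a halving of the recorded failure rate, would only restate an assumed share of one half.

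Only secondary outcomes are affected; the primary outcome and the sample size stand. The definitions are worth correcting because the change is small and uses data the plan already compiles.

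**What to change.** Make two changes to the outcome wording in section 2.0.

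- Outcome 15: count patients with a repeat parathyroidectomy from the index procedure to one stated end date, the same in both arms, and reconcile that date with the follow-up described in sections 6.0 and 10.0. Month 6 fits the present schedule. If the sponsor keeps month 12, name chart review at month 12 as the source.
- Outcome 3: state that, for analysis, a patient reoperated for persistent disease before the month-6 assessment counts as a failed index parathyroidectomy, whatever the month-6 values show.

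Both changes concern classification only and leave the timing and indication of any reoperation untouched. The cost is two lines of text, plus one chart review per patient if month 12 is kept. The recorded failure rate may rise slightly.
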